 - o potentially life-threatening congenital anomaly
 - o known hereditary metabolic disorder
 - o known chromosomal abnormality
 - teratogen exposure with symptomatic substance withdrawal
 - o congenital viral infections
 - microcephaly
 - Grade IV intraventricular hemorrhage (IVH) or seizures documented within first 72 hours of birth
 - Critically-ill with life expectancy less than 72 hours
 - Unable to obtain consent within 72 hours of birth
 - Enrolled in another intervention trial

Participant recruitment: Parents or guardians of infants who meet study criteria will be approached regarding the study as early as possible within 72 hours of the infant's birth. Informed consent will be obtained by study investigators and coordinators. Permission will be requested to re-contact the families after completion of the supplementation study for follow-up.

Randomization: As previously described by Pande et al., enrolled patients will be randomized to either the treatment group (L-carnitine, 50 µmol/kg/day) or placebo group (5% glucose, similar volume as the L-carnitine group).²⁸ Patients who meet study entry criteria and have signed informed parental/guardian consent will be enrolled in the study. Because gestational age and small for gestational age (SGA) status will impact our outcome measures, we will ensure they are equally distributed in the arms of the study by stratifying based upon these variables. We will analyze the two study arms using an intent-to-treat analysis. Therefore, enrolled patients will be stratified into fourgroups: gestational age 23 to 26 6/7 weeks, gestational age 27 to 29 6/7weeks, gestational age 30 to 31 6/7 weeks and small for gestational age (SGA). Patients within each stratum will be randomized by the pharmacist using a computerized block-generation with sets of 4. In the case of multiple births, all infants must meet study criteria, and the infants will be randomized as a set. One infant of the multiple-birth set will be randomly chosen for inclusion in the analysis. A recruitment log of all screened infants will be maintained. Clinicians and the nursing staff will be unaware of the arm of the treatment protocol to which the patient is assigned. Codes will be unblinded only after all patients have reached the study end-point, or at the request of the Data Safety Monitoring Board.

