- 1. Patient demographics: date of birth, birth weight, gestational age as determined by best obstetric estimate or Ballard score, SGA or LGA status, Apgar scores, birth history, delivery room management, gender, ethnicity.
- 2. Maternal characteristics: maternal age, maternal language, ethnicity, presence of prenatal care, type of insurance coverage, maternal educational status, presence of maternal depression, teratogen exposure (alcohol, tobacco or illicit drug use during pregnancy), antenatal steroid use, hypertension/pre-ecclampsia, gestational diabetes/Type I or II diabetes, and maternal infections.
- 3. Management of fluid and nutrition: daily fluid intake and urine output, glucose infusion rate, total caloric intake, total protein intake, and food efficiency (weight gain divided by caloric intake) while on study supplement.
- 4. Hospital course:
 - a. Growth parameters: weight, length and head circumference at birth, daily weight until birthweight regained and then weekly, weekly length, and head circumference two times per week for four weeks)
 - b. Cardiovascular: need for vasopressors, presence of PDA (including medical or surgical treatment; platelet count and mean fluid intake at time of treatment)
 - c. Gastrointestinal: feeding intolerance, NEC, presence of gastrointestinal reflux,
 - Neurological: results of aEEG readings, results of head ultrasounds including presence of germinal matrix/intraventricular hemorrhage and periventricular leukomalacia, cranial MRI results
 - e. Opthalmological: grade of retinopathy of prematurity and treatment or ophthalmologic diagnosis,
 - f. Hematologic: transfusion history including dates
 - g. Infectious disease: presence of concurrent presumed and proven infection,
 - h. Other: performance of any surgical procedures, duration of intravenous access, use of medications, and hearing screen results (OAE and/or ABR) with observed thresholds of hearing frequencies.
 - i. Clinical Risk Index for Babies (CRIB) scores will be calculated for each infant.
 - j. We will also monitor for possible short-term side effects.
- 5. Discharge information: weight, length, head circumference, and diagnoses at time of discharge, routinely-ordered discharge brain MRI findings
- 6. Neurodevelopmental assessment:

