We will assess neurodevelopmental outcomes at 18-24 months corrected age using the Bayley Scales of Infant and Toddler Development, Third Edition (BSID-III). The BSID-III is a validated instrument used for assessing the development of Cognitive, Language (Receptive and Expressive), Motor (Fine and Gross), Social-Emotional and Adaptive skills in infants and toddlers. This normative assessment yields scaled scores, composite scores, percentile ranks, and developmental age equivalents, all of which provide important information about a child's level of functioning relative to his or her same-age peers. While Cognitive, Language and Motor skills are assessed through direct interaction with the child, Social-Emotional and Adaptive skills are obtained from parent report. Because the BSID-III is commonly used for identifying children who are in need of early intervention due to developmental delays, this instrument will be sensitive to detecting the types of developmental issues we often see in very young children born preterm. Additionally, at the follow-up visit at 18-24 months corrected age, we will administer two parental questionnaires: the Modified Checklist for Autism in Toddlers (M-CHAT) and the Child Behavior Checklist (CBCL). M-CHAT is a parent-report checklist developed to screen children for early signs of autistic features. The CBCL is a standardized, well-validated parent-report questionnaire developed to assess various maladaptive behavioral and emotional problems in young children.

Record confidentiality: Records relating to the study will be kept in a secure location, to which only study personnel will have access. Records will be kept in a locked file cabinet in the neonatology offices and in a password-protected computer.

Statistical Analyses:

Statistical analysis will be performed with the assistance of a statistician.

Sample size:

We plan to recruit a total of 150 infants for our study over approximately 36months' time. This number is based upon an expected attrition of approximately 50 infants over the course of the study and a desired sample size of 100 infants. The inclusion of 100 infants in our study (50 in each study arm) will allow us to detect a moderate difference in our primary outcomes at a significance level of 0.05 with a power of 0.8. (0.5 SD; α = .05; power = .80).

Primary Outcomes	Mean	Standard Deviation	0.5 x Standard Deviation
Percent weight loss*	10.8%	6.2	3.1
Time to regain	11.3 days	4.3	2.2
birthweight*			

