NNNS Scores**			
Habituation	7.91	1.14	0.57
Attention	5.30	1.04	0.52
Arousal	4.16	0.81	0.41
Regulation	5.00	0.82	0.41
Handling	0.27	0.27	0.14
Quality of Movement	3.81	0.78	0.39
Excitability	4.23	2.10	1.05
Lethargy	6.32	3.24	1.62
Nonoptimal Reflexes	4.32	1.73	0.87
Asymmetry	1.93	1.33	0.67
Hypertonicity	0.07	0.26	0.13
Hypotonicity	0.55	0.76	0.38
Stress Abstinence	0.15	0.05	0.03

Power Calculation:

*Data available from Jack D. Weiler NICU retrospective analysis (2010)

**Tronick, E. Z., K. Olson, et al. (2004). "Normative neurobehavioral performance of healthy infants on the Neonatal Intensive Care Unit Network Neurobehavioral Scale." Pediatrics 113(3 Pt 2): 676-678.

Baseline Comparability:

Distribution of all variables will be examined for normality. Mean (continuous variables), or median (ordinal data and not normally distributed data) will be used as measures of central tendency. Range, percentiles, variance and standard deviation will be used as measures of dispersion. Standard error of the mean and 95% confidence intervals will be calculated to estimate the true populations mean for the placebo and the carnitine supplemented group. Frequency distribution will be presented as grouped, as well as relative frequency. Bivariate distributions will be presented using contingency tables. Descriptive statistics of infant's characteristics at baseline will be compared between carnitine supplemented and placebo group using t-tests for continuous variables (birthweight, age at enrollment) and chi-square test for categorical variables (race, sex, prenatal care, multiple gestation, type of delivery).

Outcome Measures:

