The effect of L-carnitine supplementation on outcome measures in enrolled infants will be examined for significance by comparing the two groups using unpaired data analysis with the assistance of a statistician. Continuous data (percent weight loss, time to regain birthweight, NNNS score, BSID-III scores) will be compared between the "placebo" and the "carnitine supplemented" groups by unpaired student t-test (a 2 tailed P value <0.05 will be considered to indicate statistical significance) or Wilcoxon's rank sum test for non-parametric parameters. Unmatched nominal data will be compared using Fisher's Exact Test or Chi-square test as required (e.g.: presence or absence of normalization of the carnitine profile; or presence or absence of pathological findings on the discharge MRI). Logistic regression models will be used to adjust for potentially confounding factors including gestational age, birth weight, race, gender, Apgar scores.

Risks and Discomforts:

A brief description of the risks and discomforts associated with this study is included in the protocol consent form and will be discussed in detail with each family at the time of study enrollment.

Carnitine is routinely administered with parenteral nutrition in approximately one-third of the neonatal intensive care units in the United States, although not in the Jack D. Weiler Hospital or Montefiore North Division NICU's. Carnitine is FDA-approved, and there have been no reports of severe toxicity from

overdose. Data available from the adult literature reports side effects of mild gastrointestinal symptoms such as gastritis, vomiting, diarrhea or abdominal cramping; body odor; and seizures, in patients with or without a known seizure disorder. These side effects are dose-dependent and might be avoided by slow consumption of the solution or greater dilution. One investigator reported transient elevation of triglycerides and increased platelet aggregation in uremic patients with severe renal insufficiency who received high doses of carnitine supplementation.⁵²

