The DSMB will review all adverse events as described in the Charter. All unanticipated problems will be reported to the DSMB and IRB within 5 days of the PI becoming aware of the problems.

With the upcoming revisions in the IRB AE reporting policy, we have decided to not follow the current IRB adverse event reporting policy dated 2008; instead we will report AEs to the IRB as follows:

- 1. Unanticipated Problems defined as anyevent, deviation, or problem
 - thatmeetsallofthefollowingcriteria:
 - unanticipated; AND
 - possibly,probablyordefinitelyrelatedto studyparticipation;AND
 - fatal,life-threatening,orseriousORsuggestsgreaterriskofharmtostudy participant(s)or othersthanwaspreviouslyknownorrecognized
- 2. Deathofaparticipantifitoccurswithin30 daysofadministrationofthestudymedication
- 3. AProtocolDeviation or an incident, experience,oroutcomethatmayplacetheparticipantorothersatgreatermedical, physiological,socialriskoreconomicriskthanwaspreviouslyknownorrecognized
- 4. AnydeviationfromIRBorInstitutionalPolicyorProcedurewhichhasthepotentialto adverselyimpactoneormoresubjectsortheoverallintegrityofdatacollected
- 5. AnyreportingthattheIRBcitesasaconditionofapprovaloftheprotocol
- 6. Complaintfromaparticipantorotherindividualwhenthecomplaintindicates unexpectedrisksorthecomplaintcannotberesolvedbytheresearchteam

- 7. DeviationfromtheIRBInformedConsentPolicy
- 8. Systematicdatacollectionerrors
- 9. Breachofconfidentiality

It is well-known that the very preterm, low birth weight infants included in this study have increased mortality compared to full-term infants. Review of our own Weiler NICU data in 2010 revealed a high mortality rate ininfants less than 30 weeks gestational age: approximately 75% for infants of gestational age of 23 weeks, 24% for gestational age 24-26 weeks, and 5% for infants of gestational age 27 – 29 weeks. Thus, we expect similar rates in infants enrolled in our study.

An additional amount of blood will be drawn as part of the study protocol. The estimated amount of blood is approximately $200 - 300 \mu$ I two to three times over the course of the study. The blood draw will be obtained with other routine bloodwork whenever possible in order to avoid additional discomfort to the infant.

Benefits:

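### The continuous primary outcomes are tested without the randomisation strata, and the only adjusted model named is logistic

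*Combined protocol and SAP*

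**What the plan says.** The Randomization paragraph gives its reason for stratifying: "Because gestational age and small for gestational age (SGA) status will impact our outcome measures, we will ensure they are equally distributed". It forms four strata, three gestational-age bands and one SGA group ("gestational age 30 to 31 6/7 weeks and small for gestational age (SGA"), and randomises in blocks of 4 within each.

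Percent weight loss, time to regain birthweight and NNNS scores are the three primary outcomes. Outcome Measures treats them as continuous, together with BSID-III, and compares the arms "by unpaired student t-test (a 2 tailed P value <0.05 will be considered to indicate statistical significance", or by a Wilcoxon rank sum test for non-parametric data. Neither test uses the strata.

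After a sentence on Fisher's exact and chi-square tests for nominal data, the section closes with its only adjusted analysis: "Logistic regression models will be used to adjust for potentially confounding factors including gestational age, birth weight, race, gender, Apgar scores". Neither SGA status nor the randomisation stratum is in that list. No linear model, ANCOVA or stratified rank test appears anywhere, and no cut-point is defined that would make a primary outcome binary.

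**The concern.** The design balances the arms on factors the sponsor calls prognostic, and the analysis then ignores them. When arms are balanced within prognostic strata, the treatment difference varies less than an ordinary two-sample standard error implies. The test becomes conservative and the precision that stratification could have delivered is not used.

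The logistic sentence does not repair this on either reading. If it covers nominal outcomes only, the continuous primary outcomes have no adjusted analysis. If it covers all outcomes, an analyst could not apply it to the continuous ones as written.

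Power is at stake, not bias or false positives.

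**Working it through.** **1. The plan's own figure.** Sample size states 50 per arm, 0.5 SD, alpha 0.05 and power 0.80. With n per arm = 2(z_α + z_β)²/0.5²:
- two-sided: 2(1.960 + 0.842)²/0.25 = 62.8, so 63;
- one-sided: 2(1.645 + 0.842)²/0.25 = 49.5, so 50.

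The stated 100 matches a one-sided test. Under the two-tailed test in Outcome Measures, power at 50 per arm is Φ(0.5/√(2/50) − 1.96) = Φ(0.54) = 0.705. That mismatch is a separate matter, but 0.705 is the starting point here.

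**2. Closed form, 50 per arm, arms fully balanced within strata.** Let R² be the share of outcome variance explained by the strata (assumed). The t-test statistic then has mean 2.5 and variance 1 − R², so:
- t-test power = Φ((2.5 − 1.96)/√(1 − R²));
- stratum-adjusted power = Φ(2.5/√(1 − R²) − 1.96);
- t-test type I error = 2Φ(−1.96/√(1 − R²)).

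| R² | t-test power | adjusted power | t-test type I |
|---|---|---|---|
| 0 | 0.705 | 0.705 | 0.050 |
| 0.1 | 0.715 | 0.750 | 0.039 |
| 0.2 | 0.727 | 0.798 | 0.028 |
| 0.3 | 0.741 | 0.848 | 0.019 |

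A simulation of 100 infants without attrition (assumed stratum shares 20/30/35/15%) gave t-test type I error of 0.038, 0.027 and 0.021 at R² 0.1, 0.2 and 0.3, close to the last column.

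**3. Simulation with attrition.** Sample size expects "expected attrition of approximately 50 infants over the course of the study and a desired sample size of 100 infants", and losses partly undo the balance. So 150 infants were randomised in blocks of 4 within four strata and 100 analysed, with 10,000 trials per setting (standard error about 0.005 for power and 0.002 for type I error).

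Assumptions:
- Stratum shares are 20/35/35/10%.
- Gestational age is uniform within its band, and from 23 to under 32 weeks for SGA.
- Stratum means follow two patterns, (1, 0, −1, 1.2) and (2, 0, −1, 0), scaled to R².
- Total SD is 1 and the effect is 0.5 SD.

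The adjusted model holds arm, the four strata and gestational age in weeks. The simulated outcome depends on stratum only, so gestational age shows its cost and no benefit. The death rates come from Risks and Discomforts ("approximately 75% for infants of gestational age of 23 weeks, 24% for gestational age 24-26 weeks, and 5% for infants of gestational age" 27–29 weeks), with 2% assumed at 30–31 weeks, followed by random loss to 100. The heavy-loss row assumes retention weights of 0.2/1/1.2/0.8.

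Power, t-test / adjusted model (two mean patterns where R² > 0):

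| Losses | R² = 0 | 0.1 | 0.2 | 0.3 |
|---|---|---|---|---|
| Random | 0.700/0.692 | 0.709/0.735; 0.699/0.731 | 0.706/0.782; 0.706/0.776 | 0.716/0.834; 0.707/0.830 |
| Protocol death rates | 0.696/0.685 | 0.704/0.729; 0.712/0.737 | 0.718/0.778; 0.716/0.777 | 0.719/0.828; 0.734/0.835 |
| Heavy loss, lowest band | 0.692/0.681 | 0.712/0.733; 0.717/0.729 | 0.717/0.778; 0.745/0.783 | 0.725/0.828; 0.763/0.829 |

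**4. Rank tests, protocol death rates.** Wilcoxon / van Elteren power is 0.676/0.653 at R² = 0; 0.679/0.698 and 0.689/0.711 at 0.1; 0.689/0.752 and 0.696/0.753 at 0.2; 0.689/0.804 and 0.713/0.808 at 0.3.

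**5. Type I error, protocol death rates, R² 0.1 to 0.3.** The t-test runs from 0.045 down to 0.029, the adjusted model from 0.050 to 0.052, and van Elteren from 0.050 to 0.051. With coarse data (5,000 trials), van Elteren gave 0.048 and 0.043 for a yes/no score with mean about 0.07, and 0.051 and 0.054 for a Poisson score with mean about 0.55 (strata not prognostic, then prognostic).

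**6. Which test for which outcome.** A non-negative score with mean below 1.5 SD would have more than Φ(−1.5) = 6.7% of a normal curve below zero. Mean/SD from the plan's power table:
- below 1.5: Asymmetry 1.93/1.33 = 1.45; Handling 0.27/0.27 = 1.00; Hypotonicity 0.55/0.76 = 0.72; Hypertonicity 0.07/0.26 = 0.27;
- above 1.5: percent weight loss 10.8/6.2 = 1.74; time to regain birthweight 11.3/4.3 = 2.63; every other NNNS score at least 1.95 (Lethargy, 6.32/3.24).

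**The case against.** An unadjusted primary comparison is a legitimate choice, and this one inflates nothing. The gain depends on an R² that the documents do not give. At R² = 0.1 it is only 0.01 to 0.03, and at zero it is a small loss. This stands, and it is why the power figures are illustration only.

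The logistic sentence directly follows the one on nominal data, so it most naturally covers those outcomes, for which it is correct. Its covariate list is also worded as non-exhaustive, and gestational age, birth weight and gender carry much of what SGA status conveys. Both points are fair. But on that reading the primary outcomes still have no adjusted analysis, although the sponsor states that the strata affect them.

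The two weight outcomes are observed early, so more than 100 infants may contribute. On the assumed shares, expected mortality is 0.20 × 0.3675 + 0.35 × 0.05 + 0.35 × 0.02 + 0.10 × 0.184 = 0.116, leaving about 133 of 150. Here 0.3675 = (0.75 + 3 × 0.24)/4 and 0.184 = (0.75 + 3 × 0.24 + 3 × 0.05 + 2 × 0.02)/9. At 65 per arm, t-test power with no stratum effect is 0.81. This raises the baseline but does not remove the gain: at R² = 0.2 the step 2 formulas, with 0.5/√(2/65) = 2.85 in place of 2.5, give 0.840 against 0.890. Analysing one infant per multiple birth would pull the number back down.

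Siblings randomised as a set may differ in SGA status, and the plan does not say which stratum the set enters. The simulation does not model this. Using the stratum actually recorded at randomisation avoids having to reconstruct it.

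**Conclusion.** The concern holds. The plan randomises by strata it calls prognostic, tests its continuous primary outcomes without them, and names no adjusted model that fits those outcomes.

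Under random loss or the protocol's death rates, adjustment adds about 0.03, 0.06 to 0.08 and 0.10 to 0.12 of power at R² 0.1, 0.2 and 0.3. With heavy loss of the lowest gestational-age band it adds 0.01 to 0.02, 0.04 to 0.06 and 0.07 to 0.10. If the strata explain nothing, the cost is about 0.01 for the linear model and 0.02 for van Elteren. These sizes rest on assumed R², stratum shares and loss patterns. The inconsistency in the text does not.

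The planned test is not wrong in level, so this is a correction the sponsor should make, not a threat to validity. Nor does it reliably cure the shortfall in step 1: in closed form, 50 per arm reaches 0.80 two-sided only if R² is about 0.20 or more.

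**What to change.** Before unblinding, amend Outcome Measures to fix one primary test per continuous outcome:
- **(a)** a linear model with arm, the four-level stratum as recorded at randomisation, and gestational age in weeks (included because the SGA stratum spans all gestational ages); or
- **(b)** a van Elteren test stratified by the same four strata, for outcomes that would otherwise have gone to Wilcoxon.

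One workable assignment sends Handling, Asymmetry, Hypotonicity and Hypertonicity to (b), and percent weight loss, time to regain birthweight and the remaining NNNS scores to (a). The 1.5 SD cut-off is a reviewer's choice, and the NNNS figures come from healthy infants. The sponsor may use another list if it is fixed in advance. Either way, the list replaces a choice of test that now follows inspection of the data (Baseline Comparability: "Distribution of all variables will be examined for normality").

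State that logistic regression applies to binary outcomes only, and keep the unadjusted tests as sensitivity analyses.

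The cost is SAP wording and a few lines of code. The case report form already holds "gestational age as determined by best obstetric estimate or Ballard score, SGA or LGA status", and the stratum is known from randomisation. The downsides are the small power loss if the strata are not prognostic and the usual linear-model assumptions. The change does not settle how infants who die before regaining birthweight are counted. If they are ranked worst, that outcome belongs in (b), so the sponsor should decide this at the same time.

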We hypothesize that preterm infants supplemented with early physiologic doses of L-carnitine while on parenteral nutrition will have improved short-term growth parameters and significantly higher neurobehavioral scores when compared with control infants.

Primary Aims:

To determine whether carnitine supplementation is associated with:

- 1. Decreased percent weight loss within the first two weeks of life and decreased length of time to regain birthweight.
- 2. Improved performance on the NICU Network Neurobehavioral Scale (NNNS) at 40 weeks postmenstrual age (+/- 2 weeks).

Secondary Aims:

To determine whether carnitine supplementation is associated with:

- 1. Increased rate of growth of head circumference within the first month of life and increased food efficiency (weight gain/calorie intake) during the supplementation period.
- 2. Normalization of the serum carnitine profile at two weeks of life, compared with infants born at a post-menstrual age 2 weeks later.
- 3. Enhanced brain maturation as measured by amplitude-integrated EEG (aEEG) measurements obtained during the hospital course
- 4. Fewer abnormal findings, better brain growth, white matter development and brain metabolism on brain magnetic resonance imaging (MRI) at 36-40 weeks' corrected age (prior to hospital discharge)

Because of the potential for systemic effects of L-carnitine supplementation, we will also monitor those variables which showed significant difference in our prior study: rates of proven infection, hearing screen failure and PDA ligation.

Primary Outcomes:

- 1. Length of time to regain birthweight,
- 2. Percent weight loss in the first two weeks of life,
- 3. Neurodevelopmental scores on the NICU Network Neurobehavioral Scale (NNNS) at 40 weeks post-menstrual age (+/- 2 weeks)

Methods/Design:

This is a prospective, randomized controlled clinical trial involving infants with gestational age (GA) <32 wks who are born at either the Jack D. Weiler Hospital or the Wakefield Division of Montefiore and admitted to theirNeonatal Intensive Care Unit. Informed consent will be obtained from the parents of eligible patients as early as possible within 72 hours of birth. Infants whose parents have signed an informed consent form will be randomized to receive either carnitine supplementation (50 µmol/kg/day) versus placebo within 72-96 hours of birth.

Inclusion criteria:

- Infants born <32weeks' gestation
- Exclusion criteria:
 - Presence of

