These measurements will be obtained through brain MRIs routinely obtained in preterm infants prior to discharge. There will be no change in the routine protocol in order to obtain these outcomes. The reading and analyses of these MRIs will be performed at no additional cost to the study subject.

Neurobehavioral Assessment:

Infants discharged from the Weiler and Montefiore North Division NICUs routinely follow-up with our neonatologists at term-equivalent age. At this visit, the infants routinely receive a neurobehavioral

assessment. We have chosen to administer the NICU Network Neurobehavioral Scale due to its prevalence of use in neonatal research and its strong psychometric properties.⁴⁹

The NICU Network Neurobehavioral Scale (NNNS) was developed by [name]., & [name].⁵⁰ The scale is intended for use with use with healthy and at-risk preterm infants and full term infants at risk because of prenatal substance exposure or other conditions. The NNNS can be utilized in either a clinical or research setting in order to obtain a comprehensive assessment of neurobehavioral functioning. There is a focus on neurologic, stress, and withdrawal signs. The tool may be used with infants through 6 weeks of age and may be used as early as 30 weeks for preterm infants. The exam assesses 115 items in three categories:

- Neurological items: active and passive muscle tone, primitive reflexes, and central nervous system integrity
- Behavioral state, sensory, and interactive responses
- Stress/abstinence items

The examiner assesses the items. Summary scores are generated for stress, withdrawal, and the major domains of neurobehavioral performance. The NNNS is administered in a standardized format which allows objective assessment of the infant. Normed scores are available for at-risk and healthy infants. Because the assessment is relatively new, there are no long-term studies looking at predictive validity. However, the test is based upon a variety of prior tools, where long-term predictive validity has been shown.⁵¹ The test takes approximately 20 minutes to administer. (Ordering information: http://www.brookespublishing.com/store/books/lester-7659/index.htm)

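### The NNNS primary outcome is not defined as one test, and no rule links the three primary outcomes

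*Combined protocol and SAP*

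**What the plan says.** The Primary Outcomes list has three entries: time to regain birthweight, percent weight loss in the first two weeks, and "Neurodevelopmental scores on the NICU Network Neurobehavioral Scale (NNNS) at 40 weeks post-menstrual age (+/- 2 weeks". The Primary Aims place the two growth outcomes in one aim ("Decreased percent weight loss within the first two weeks of life and decreased length of time to regain birthweight") and the NNNS in a second.

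Neurobehavioral Assessment describes the instrument as yielding several results: "Summary scores are generated for stress, withdrawal, and the major domains of neurobehavioral performance". It describes no total score. The table headed Primary Outcomes, under Sample size, has two growth rows and 13 NNNS rows, from Habituation to Stress Abstinence, each with its own SD and half-SD target.

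Outcome Measures then treats the NNNS as a single quantity: "Continuous data (percent weight loss, time to regain birthweight, NNNS score, BSID-III scores) will be compared" by t-test or rank-sum test, and "a 2 tailed P value <0.05 will be considered to indicate statistical significance".

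Sample size states that 100 infants, 50 per arm, will allow the trial to "detect a moderate difference in our primary outcomes at a significance level of 0.05 with a power of 0.8", for a 0.5 SD difference. It does not say whether that level is one- or two-sided.

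The document gives no lead NNNS scale, global test, testing order or multiplicity adjustment, and it does not say which primary outcomes must succeed.

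**The concern.** The third primary test cannot be run as written. Outcome Measures needs one score, and no section supplies it. Nor can the scales simply be added. The Hypothesis expects higher scores with carnitine, yet rows such as Nonoptimal Reflexes and Asymmetry have names that suggest higher is not better, and the document does not give each scale's favourable direction.

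With the choice open, one scale could be picked after unblinding and reported as the NNNS result. The missing success rule adds to this: a reader cannot tell whether one significant primary outcome, both growth outcomes, or growth together with NNNS would count as a positive trial. These are the confirmatory outcomes, and the Benefits section foresees a possible change in nutritional recommendations.

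**Working it through.** **Inputs.** Two-sided 0.05 per comparison (Outcome Measures); three primary outcomes (Primary Outcomes); 13 NNNS scales (Primary Outcomes table); 50 per arm, 0.5 SD, power 0.80 (Sample size). The documents give no correlations between outcomes, so equal correlations of 0.3, 0.5 and 0.7 are assumed, with independence shown for reference.

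**1. The plan's own power figure.** The noncentrality is 0.5 × √(50/2) = 2.5.
- Two-sided 0.05: Φ(2.5 − 1.960) = 0.705; by the t distribution, 0.697.
- One-sided 0.05: Φ(2.5 − 1.645) = 0.804; by t, 0.799.

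The stated 0.80 reproduces only one-sided. With the two-tailed test that the plan specifies, power is about 0.70, and 0.80 needs 2(1.960 + 0.842)²/0.5² = 62.8, so 63 per arm (normal approximation). At the strictest Holm step for three tests (0.05/3 = 0.0167), power at 50 per arm is 0.528 by t.

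**2. Chance of at least one P<0.05 when no outcome has an effect.** For k independent tests it is 1 − 0.95^k. For equal correlation ρ and c = 1.96, it is 1 − ∫[Φ((c − √ρ·x)/√(1−ρ)) − Φ((−c − √ρ·x)/√(1−ρ))]^k φ(x)dx.

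| Tests | Independent | ρ = 0.3 | ρ = 0.5 | ρ = 0.7 |
|---|---|---|---|---|
| 13 NNNS scales, any one | 48.7% | 41.8% | 33.4% | 24.1% |
| 3 outcomes (one NNNS score), any one | 14.3% | 13.6% | 12.5% | 10.9% |

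The 13 scales come from one examination ("The test takes approximately 20 minutes to administer"), so some correlation is likely and 48.7% is a high-end value. Even at ρ = 0.9 the 13-scale figure is 13.8%. The three-test figure cannot exceed 3 × 0.05 = 15% under any dependence.

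**3. If aim 1 needs both growth results, or NNNS succeeds.** With one NNNS score independent of growth, the error is p + 0.05 − 0.05p, where p is the chance that both growth tests are significant. At growth correlation 0, p = 0.0025 and the error is 5.2%. At 0.7, p = 0.10 − 0.0835 = 0.0165 and the error is 6.6%. If any of 13 scales can serve as the NNNS result, it is 24–43% (ρ = 0.7 to 0.3).

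**4. If growth and NNNS must both succeed.**
- Both growth results required: the error cannot exceed 5%, because one named 5% test must always be passed.
- Either growth result enough, growth independent of NNNS: 0.0835 × 0.2407 = 2.0% at ρ = 0.7, up to 0.0975 × 0.4867 = 4.7% under independence.
- Either growth result enough, all 15 statistics sharing one correlation: 0.0951 + 0.4182 − 0.4574 = 5.6% at 0.3, and 0.0835 + 0.2407 − 0.2565 = 6.8% at 0.7.

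So there is no material inflation when nothing works. Now suppose growth truly improves by 0.5 SD on both measures. At 50 per arm and growth correlation 0.5, both growth tests succeed with probability 0.552. With any of 13 null scales counting, independent of growth, the chance of a false NNNS success within a positive trial is 0.552 × 0.241 = 13% to 0.552 × 0.418 = 23%. It approaches 24–42% as growth success becomes certain.

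**The case against.** The best defence is that the text already points to a narrower reading. The Hypothesis joins better growth and higher NNNS scores with the word and, aim 1 does the same for its two growth outcomes, and Outcome Measures speaks of one NNNS score. On that reading the error rate is modest. This deserves weight, and it is why the larger percentages are conditional. But a hypothesis or aim is not a decision rule, and a singular noun does not say which of 13 scales it means.

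A second defence is that growth and neurobehavior are separately numbered aims, and testing distinct questions each at 0.05 is a recognised position. That stands in part: Holm across all outcomes is one defensible choice, not an obligation. The plan would still have to say which position it takes.

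Third, the rates count results in either direction, while the aims are directional. For three tests, a false claim of benefit runs at about 5–7%, against a nominal 2.5%. The inflation is real, but the absolute risk of wrongly claiming benefit is about half the two-sided figure.

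A reader might go further and infer that all 15 table rows are tested and any one counts, giving 26–46% with equal correlations throughout, or 30–47% with growth independent of NNNS. The documents do not support this as a statement of the plan: the table serves the power calculation, and no text says that every row is tested or that one success is enough.

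**Conclusion.** The concern holds in this form: the NNNS primary outcome is not one defined test, and nothing links the three primary outcomes. The first part needs no assumption; it follows from setting the outcome list, the power table and the analysis text side by side. The error rates are illustrations. They assume no true effects, two-sided tests, jointly normal statistics and correlations that the documents do not give: about 24–42% if any of 13 scales may stand as the NNNS result, and at most about 14% with one NNNS score and any of three outcomes counting. It would go too far to say that the plan has a 26–46% false-positive rate, or that it must use Holm. The definition of the NNNS test is the firmest part and must be settled before unblinding. The power discrepancy (0.70 against 0.80) is a linked correction that stands on its own and adds nothing to the error-rate argument.

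**What to change.** Before unblinding:

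1. **Name one primary NNNS test.** Use one scale, or one pre-specified global test such as O'Brien's rank-sum. A global test needs each scale's favourable direction, taken from the scoring manual, and a rule for infants with missing scales. Report the other scales as supportive, with confidence intervals and no significance claim.
2. **State one success rule that controls the overall two-sided error at 0.05.** Holm across three outcomes, a fixed order, or both growth outcomes required with Holm across the two aims would each do. The choice is the sponsor's.
3. **Restate the power under Sample size.** For 0.5 SD at 50 per arm it is about 0.70 two-tailed, and about 0.53 at the strictest step if Holm across three is chosen.

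Power of the three rules at 50 per arm, t-tests, one named NNNS scale, and growth correlation 0.5:

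| Rule | All three effects 0.5 SD | NNNS power if only NNNS works |
|---|---|---|
| Holm across three | about 0.61 each | 0.53 |
| Fixed order (time, weight loss, NNNS) | 0.70, 0.55, 0.39 | about 0.01 |
| Both growth required, Holm across aims | 0.50 (aim 1), 0.63 (NNNS) | 0.59 |

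The cost is lower stated power per outcome; no new infants or data are needed. At the strictest Holm step, the difference detectable with 0.80 power rises from 0.57 to 0.66 SD at 50 per arm (0.657 × 6.2 = 4.1 percentage points; 0.657 × 4.3 = 2.8 days). Growth is measured early, while the plan spreads its "expected attrition of approximately 50 infants over the course of the study", so more than 50 per arm may have growth data. At an assumed ceiling of 75 per arm, power falls from 0.86 to 0.74 and the detectable difference rises from 0.46 to 0.53 SD (3.3 points; 2.3 days). Early deaths and the rule of analysing one infant per multiple-birth set keep the real number below 75. The power of a global NNNS test depends on correlations that the documents do not give.
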